1.0 BACKGROUND AND SIGNIFICANCE

1.1 Chemotherapy and Radiation Therapy for Diffuse Large B-Cell Lymphoma

Based on two randomized studies performed in the 1980s and 1990s (1, 2), chemotherapy followed by involved-field radiation therapy has become a standard treatment for patients with early-stage diffuse large B-cell lymphoma (DLBCL). In these studies, chemotherapy consisted of CHOP (cyclophosphamide, doxorubicin, vincristine, and prednisone). Radiation therapy (RT) consisted of 30 Gy in the ECOG study (1) after eight cycles of CHOP and 40-55 Gy in the SWOG study (2) after 3 cycles of CHOP. Our practice at Duke, which is consistent with guidelines set forth by the National Comprehensive Cancer Network, is to treat patients who achieve a complete response after 4 to 6 cycles of chemotherapy with radiation therapy, 30 Gy, to originally involved sites.

Chemotherapy is the cornerstone of treatment for patients with stage III-IV DLBCL, and the role of consolidation RT is not well defined. Retrospective studies evaluating the role of RT are conflicting (3, 4). The only randomized phase III trial is the one carried out by Aviles et al. This study demonstrated improved event-free survival and overall survival for patients with stage IV DLBCL who received radiation therapy to original sites of bulky disease after achieving a complete response to chemotherapy (5). Currently, we do consolidate with radiation therapy selected patients with advanced DLBCL with radiation therapy who achieve CR with chemotherapy. These patients are generally treated to all sites of original disease if practical (as opposed to just bulky sites).

While CHOP is the most common regimen used for DLBCL, other regimens have been found to be equally effective (6). At Duke, the vast majority of patients are treated with rituximab and CHOP (R-CHOP), though other regimens are occasionally employed based on medical comorbidities and side effect profile.

1.2 Rituximab for DLBCL

Since the initial studies of radiation therapy in early stage DLBCL were performed, the standard therapy for DLBCL has been significantly improved with the addition of rituximab to the standard CHOP regimen. Several randomized studies have evaluated CHOP versus R-CHOP showing a significant improvement in both progression-free survival and overall survival with the addition of rituximab (7, 8). As a result of more effective chemotherapy regimens, a lower dose of consolidation radiation therapy than has previously been studied may be effective.

1.3 PET Assessment after Chemotherapy

Positron emission tomography (PET) scans have become standard in lymphoma management to both assess disease extent at diagnosis as well as evaluate response to therapy. Patients treated with chemotherapy alone who have not achieved a complete response by PET are at substantially higher risk of relapse compared with patients who have a negative post-chemotherapy PET(9-11). A positive PET is also associated with an increased risk of local failure after chemotherapy and consolidation RT. In a study from Duke, patients with a positive post-chemotherapy PET were at higher risk of in-field failure compared with patients with a negative post-chemotherapy PET after administration of consolidation RT(12). Four-year in-field control was 97% with a negative PET versus 81% with a positive PET ($p<0.01$). The median RT dose was 30 Gy. Thus, PET scans help discriminate patients who have not had an optimal response to chemotherapy and are at increased incidence of disease relapse after a combined modality regimen. These patients may require a higher dose of consolidation radiation therapy and would not be candidates for this study. PET interpretations be standardized based on the Deauville Criteria. In the setting of combined modality therapy, a Deauville score of 1-3 is currently considered negative and a Deauville score of 4-5 is currently considered positive.

1.4 Risk of In-field Failure after Combined Modality Therapy

In-field failure (disease recurrence within the radiation field) is rare after combined modality therapy. In three large randomized trials, crude in-field failure rates after CHOP and radiation therapy (30 to 40 Gy) ranged between 4% and 7% (1, 13, 14). In these studies, rituximab was not administered and PET scans were not used to assess response to chemotherapy prior to consolidation RT.

1.5 Rationale for Radiation Therapy Dose Reduction

There are no prospective studies in DLBCL guiding the appropriate dose that should be used after effective chemotherapy. In Hodgkins lymphoma, the German Hodgkin Study Group HD10 recently demonstrated that 20 Gy was as effective as 30 Gy after 2-4 cycles of ABVD in patients with early-stage, favorable disease (ASH 2009). The risk of complications related to radiation therapy, including cardiac disease and secondary cancers, appear to be related to both dose (15) and volume (15, 16). If the dose and volume of radiation therapy can be reduced, while maintaining high rates of disease control, this would undoubtedly decrease the risk of side effects and long-term risks.

1.6 Rationale for Radiation Therapy Field Reduction

There is no consensus as to the optimal RT field size for patients with DLBCL. Many institutions follow the pattern used for Hodgkins lymphoma, namely treating an involved field (i.e., a region as opposed to true anatomic extent of disease) (17). However, several cooperative groups and institutions currently treat only originally involved sites (as opposed to regions). For example, in a retrospective analysis from the University of British Columbia of patients treated with combined modality therapy for DLBCL (3 cycles of CHOP +/- rituximab), the local control rate was equivalent between involved field and involved node treatment volumes (18). Only 2% of patients developed a marginal recurrence, defined as a recurrence outside the involved nodal field but within what would have been encompassed with an involved field. The same group has recently reported similar findings for Hodgkin's Disease (19). In this study, we will treat the original anatomical extent of disease and not attempt to treat sites which were not clinically involved at diagnosis. The hypothesis being, that chemotherapy can successfully eradicate microscopic disease, and consolidation RT will be utilized to help control gross disease.

2.0 PURPOSE

This phase II study will evaluate whether a reduction in the RT dose, concomitant with a decrease in the RT field size, in patients that achieve CR and have a negative post-chemotherapy PET scan following 4 to 6 cycles of rituximab containing chemotherapy, will be associated with a low risk of in-field failure. The goal of this approach is to maintain excellent control rates while minimizing the risk of acute and late toxicity.

2.1 Hypothesis

Hypothesis- After more effective systemic therapy (employing rituximab), with confirmation of optimal response to chemotherapy (Deauville score of 1-3 on post-chemotherapy (or interim) PET scan), the RT dose and treatment volume can be safely reduced from 30 Gy to 20 Gy while maintaining high rates of local control.

3.0 OBJECTIVES

3.1 Primary Objective

To determine if high rates of local control can be maintained after a reduction in the RT dose and volume after 4 to 6 cycles of rituximab containing chemotherapy.

3.2 Secondary Objectives

3.2.1 To determine the progression-free survival and overall survival after chemotherapy and low-dose (20 Gy) consolidation radiation therapy.

3.2.2 To identify patterns of failure after low-dose, reduced volume consolidation radiation therapy.

4.0 PATIENT RECRUITMENT

This is a prospective, phase II, single arm study. Ascertainment of eligibility will be determined by review of the records of patients with DLBCL seen by radiation oncology PI, co-investigator or other clinical faculty of radiation oncology. The subject population (with no gender or minority restrictions) will include adult patients meeting the eligibility criteria. Inclusion of women and minorities is encouraged. All patients must sign an IRB-approved informed consent prior to enrollment. Eligibility of patients will be ascertained by reviewing necessary portions of the medical record.

5.0 PATIENT SELECTION

5.1 Eligibility

1. Histologic documentation of diffuse large B-cell lymphoma, or any of its variants as defined in the WHO classification, including but not limited to any of the following:
 - a. DLBCL NOS
 - b. Primary mediastinal DLBCL
 - c. T cell/histiocyte-rich large B-cell lymphoma
2. Completion of at least 4 cycles of a rituximab-containing, anthracycline-based combination chemotherapy regimen no sooner than 3 weeks and no longer than 8 weeks prior to the start of radiation therapy
3. Deauville score of 1-3 on post-chemotherapy (or interim) PET scan
4. ANC \geq 1000 and platelet count \geq 40,000
5. \geq 18 years of age.
6. For females of childbearing potential, a serum pregnancy test within 2 weeks prior to registration; Note: if pelvic irradiation is to be given, the serum pregnancy test must be repeated within 48 hours prior to registration.
7. Signed study-specific informed consent.
8. For patients with HIV/AIDS, the following must be true:
 - The patient is compliant on combination anti-retroviral therapy (CART)
 - The patient has CD4 count \geq 200 at time of diagnosis

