5.2 Ineligibility

1. Any contraindications to irradiation.
2. Primary CNS lymphoma

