6.0 PRETREATMENT EVALUATION

1. A complete history and physical within 4 weeks of consent
2. Routine laboratory work including complete blood count (CBC) at least 3 weeks after chemotherapy and less than 4 weeks before beginning radiation therapy.
3. PET/CT (interim or post-chemotherapy), available for review
4. Negative serum pregnancy test for women of child-bearing potential

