7.0 REGISTRATION PROCEDURE

The patients will be recruited from the clinics by the radiation oncologist from his/her practice. Only radiation oncologists listed as Key Personnel for this study and who have completed the required ethics training may enroll patients on this study. The patient's primary medical oncologist will be apprised of the patient's intent to participate in the study. Following verification of eligibility the patient will be assigned a sequential study ID number.

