Treatment breaks due to RT-induced toxicity are expected to be rare. To be eligible for study participation, subjects must have a baseline ANC ≥ 1000 . It is very rare for patients who initiate radiation therapy with an ANC > 800 to become neutropenic during the course of treatment. The standard of care for lymphoma patients receiving chemotherapy is to continue all cycles of chemotherapy despite episodes of neutropenia unless the patients experiences an episode of febrile neutropenia (temperature greater than 100.5 degrees with an ANC ≤ 500). This study will follow the

medical oncology model and radiation treatment will continue during episodes of neutropenia, unless febrile neutropenia occurs. However, treatment breaks will be provided for thrombocytopenia, which is defined as platelets < 25,000.

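### The repeat pregnancy test required for pelvic irradiation is timed to registration, not to the first fraction, and no other provision closes the interval between the two

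*Combined protocol and SAP*

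**What the plan says.** All references are to the combined protocol and SAP.

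- **Section 5.1, criterion 6.** Women of childbearing potential need a serum pregnancy test in the 2 weeks before registration. A note adds that "if pelvic irradiation is to be given, the serum pregnancy test must be repeated within 48 hours prior to registration".
- **Section 6.0, item 4.** The pretreatment evaluation lists "Negative serum pregnancy test for women of child-bearing potential", with no date or window.
- **Section 6.0, item 2.** The blood count in the same list is dated at both ends: "at least 3 weeks after chemotherapy and less than 4 weeks before beginning radiation therapy".
- **Section 5.1, criterion 2.** Chemotherapy must have been completed "no sooner than 3 weeks and no longer than 8 weeks prior to the start of radiation therapy". Section 8.1 keeps the 3-week minimum but only strongly recommends the 8-week limit.
- **Section 7.0.** "Following verification of eligibility the patient will be assigned a sequential study ID number". No maximum time from registration to the start of radiation is given.
- **Section 5.2, item 1.** The exclusion reads "Any contraindications to irradiation". It names neither pregnancy nor a test.
- **Sections 8.1 and 9.1.** Neither the treatment section nor the list of evaluations during radiation includes a pregnancy test. Section 9.1 does include a blood count.

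**The concern.** The extra test applies only to women whose pelvis will be irradiated. Registration exposes nobody; the first fraction does. A rule meant to protect against exposure should be dated from the exposure, and here it is dated from an administrative step that may come earlier.

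If time passes between the two, a pregnancy that becomes detectable in that time would not be found by any dated test in the protocol text. The probability is low, but unrecognised fetal exposure to pelvic radiation is serious and irreversible. The protocol can tie a test to treatment, as it does for the blood count in section 6.0, so the registration anchor is not forced by the way the schedule is built.

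**Working it through.** The plan gives no figure for this interval, so there is nothing to reproduce. The check is a comparison of provisions followed by one line of arithmetic.

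**1. Is any pregnancy test tied to the first fraction?**

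| Section | Test required | Dated from |
|---|---|---|
| 5.1, criterion 6 | serum test, all women of childbearing potential | registration (within 2 weeks before) |
| 5.1, criterion 6, note | repeat test if pelvis irradiated | registration (within 48 hours before) |
| 6.0, item 4 | negative serum test | no date; the heading implies only before treatment |
| 8.1 and 9.1 | none | not applicable |

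None is. The registration test can be read as satisfying item 4.

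**2. Is the interval from registration to radiation limited?** Not directly. Section 7.0 is silent. Criterion 2 limits the time from chemotherapy to radiation, which restricts the interval only indirectly.

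**3. How old can a compliant result be at the first pelvic fraction?**

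Oldest result = test window before registration (2 days) + interval from registration to radiation.

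The second term is not in the documents and has to be assumed.

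- *Registration on the day of the first fraction:* 0 + 2 = 2 days, so the result is 0 to 2 days old and there is no gap.
- *Registration on or after the section 6.0 blood count.* This assumes that count verifies the neutrophil and platelet thresholds in criterion 4. Section 8.1 gives this some support by speaking of a baseline value: "To be eligible for study participation, subjects must have a baseline ANC". The count is at least 21 days after chemotherapy and less than 28 days before radiation. With w weeks from chemotherapy to radiation, the longest interval is the smaller of 7w − 21 days and just under 28 days.
  - At w = 3: 21 − 21 = 0, plus 2 gives 2 days.
  - At w = 7: 49 − 21 = 28, capped at just under 28, plus 2 gives just under 30 days.
  - At w = 8: 56 − 21 = 35, with the same cap, again gives just under 30 days.

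**4. What happens if the test is dated from the first fraction?** The oldest compliant result is 2 days, however long the wait after registration.

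**The case against.** The strongest reply is that the gap may hardly exist in practice. Criterion 2 is defined by the start of radiation, so verifying eligibility presupposes a known or planned start date. The pelvic clause likewise presupposes that the field is known. Section 7.0 says that "The patients will be recruited from the clinics by the radiation oncologist from his/her practice", which also makes a short interval plausible. This stands as a reason not to treat long gaps as ordinary. It does not make 48 hours a requirement.

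A second reply is that other provisions already cover the risk. Section 6.0 item 4 requires a negative result under a pretreatment heading, and can be read as a test separate from the eligibility one. Section 5.2 excludes contraindications to irradiation, and section 11.0 commits the study to radiation therapy standards. Radiation is described as standard care in sections 12.0 and 13.0, so the hazard is not created by the trial. All of this is fair, but none of these provisions sets a dated test. The exclusion acts on a known pregnancy and does not detect a new one. The content of the standards is not in the documents.

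A third reply concerns the day counts, and it is right. The figure of just under 30 days needs four things together: radiation at 7 weeks or later, a blood count almost 28 days before it, registration on the day of that count, and a pregnancy test a full 48 hours before that. The link between the section 6.0 count and criterion 4 is an inference. The figure is an illustration of what the text permits, not an estimate.

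A reader might go further and infer that pelvic treatment will routinely start on results several weeks old. One could also compute 56 + 2 = 58 days by placing registration at the end of chemotherapy and radiation at 8 weeks. The documents do not support either as a finding. They report no actual intervals, and the 58-day case also needs criterion 4 to be verified on a blood count earlier than the one in section 6.0.

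**Conclusion.** The point holds as a misplaced timing anchor. A rule triggered by pelvic exposure is dated from registration, and nothing else in the text requires a test near the first fraction. A compliant site could start pelvic radiation on a result older than 48 hours.

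How much older cannot be read from the documents. The range runs from no gap, if registration and the first fraction coincide, to an illustrative ceiling of just under 30 days under the blood-count assumption. The number of women concerned cannot be derived either. They are the women of childbearing potential receiving pelvic radiation among 62 patients, so the reach is narrow.

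It would be wrong to conclude that the protocol lacks pregnancy screening, or that the trial's results are at risk. Screening is required, and the primary endpoint, alpha and power are unaffected. The finding covers only the tests that the available protocol text requires. The consent pages were not available and may contain further instructions. Confidence is high about the anchor, but not about the size of the risk. The case for acting is that the possible harm is grave and the correction is nearly free.

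**What to change.** Make two linked edits.

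1. **Section 5.1, criterion 6.** Keep the serum test in the 2 weeks before registration as the eligibility screen. Delete the note requiring a repeat within 48 hours before registration.
2. **Section 6.0, item 4.** Keep the general requirement for a negative test and add: *for women of childbearing potential receiving pelvic irradiation, a negative serum pregnancy test within 48 hours before the first fraction; the registration test counts if it falls in that window.*

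Both edits are needed. Adding the second while leaving the existing note in place could require three tests: one within 2 weeks of registration, one within 48 hours of registration and one within 48 hours of radiation. With both edits, a woman receiving pelvic radiation needs at most two, and one if a single test falls in both windows. The window for non-pelvic treatment does not need to change.

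The cost is small. There is little or no net increase in tests. The drawback is that the repeat pelvic test can no longer be checked when the study ID is assigned, so a positive result could emerge after registration. A line saying how such a patient is handled would be sensible.

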5.2 Ineligibility

1. Any contraindications to irradiation.
2. Primary CNS lymphoma

6.0 PRETREATMENT EVALUATION

1. A complete history and physical within 4 weeks of consent
2. Routine laboratory work including complete blood count (CBC) at least 3 weeks after chemotherapy and less than 4 weeks before beginning radiation therapy.
3. PET/CT (interim or post-chemotherapy), available for review
4. Negative serum pregnancy test for women of child-bearing potential

7.0 REGISTRATION PROCEDURE

The patients will be recruited from the clinics by the radiation oncologist from his/her practice. Only radiation oncologists listed as Key Personnel for this study and who have completed the required ethics training may enroll patients on this study. The patient's primary medical oncologist will be apprised of the patient's intent to participate in the study. Following verification of eligibility the patient will be assigned a sequential study ID number.

8.0 TREATMENT

8.1 Radiation Therapy

Radiation therapy is to be initiated no sooner than 3 weeks after completion of chemotherapy. It is strongly recommended that radiation therapy start within 8 weeks of the final cycle of chemotherapy.

Equipment

All patients will be treated using conventional or three-dimensional techniques (preferred) or intensity-modulated radiation therapy via a linear accelerator using photon energies of 6 and/or 15 MV.

Treatment Planning

An immobilization device, such as a styrofoam mold or thermoplastic head mask, will be designed for each patient. Intravenous and oral contrast will be administered if necessary to optimally design the radiation fields in the absence of medical contraindications, such as an allergy to iodinated contrast.

Target Volume

Stage I-II disease- The clinical target volume (CTV) will include the original extent of disease plus a margin of 0-5 cm to account for uncertainties in defining this volume in the post-chemotherapy setting. Within the lung and abdomen, the pre-chemotherapy length but the post-chemotherapy width will be contoured as target (to protect critical structures such as lung and kidney). The CTV will be expanded by 5-10 mm to account for daily set-up error and/or target motion (such as the respiratory-induced movement of the hilum). The PTV will be expanded by 5-8 mm to account for beam penumbra when three-dimensional techniques are utilized.

Stage III-IV- Treatment volumes for patients with advanced DLBCL will be individualized based on the clinical presentation. When feasible, consolidation of all sites originally involved is encouraged. However, consolidation of only certain sites (such as sites of bulky disease) will be acceptable.

Treatment

Patients will be set up daily using on-board imaging or weekly/biweekly MV portal films. Radiation will be given with 5 fractions per week. Patients will be treated with 1.5 to 2 Gy fractions to a total dose of 18 to 20 Gy. Treatment to subportions of the target volume can be reduced if critical normal structures are in close proximity (i.e. limiting the dose to 18 Gy to the kidneys).

Treatment Interruptions during RT

Treatment breaks due to RT-induced toxicity are expected to be rare. To be eligible for study participation, subjects must have a baseline ANC ≥ 1000 . It is very rare for patients who initiate radiation therapy with an ANC > 800 to become neutropenic during the course of treatment. The standard of care for lymphoma patients receiving chemotherapy is to continue all cycles of chemotherapy despite episodes of neutropenia unless the patients experiences an episode of febrile neutropenia (temperature greater than 100.5 degrees with an ANC ≤ 500). This study will follow the

medical oncology model and radiation treatment will continue during episodes of neutropenia, unless febrile neutropenia occurs. However, treatment breaks will be provided for thrombocytopenia, which is defined as platelets < 25,000.

